7.5 Criteria for Discontinuation or Withdrawal of a Subject

The primary reason for discontinuation or withdrawal of the subject from the study or study medication should be recorded in the electronic case report form (eCRF) using the following categories. For subject failure, refer to Section 9.1.14.

1. Death. The subject died on study and caused early termination of study treatment.
Note: If the subject dies on study, the event will be considered as serious adverse event (SAE). Refer to Section 10.2.2 for the reporting procedures.
2. Adverse event (AE). The subject has experienced an AE that requires early termination because continued participation imposes an unacceptable risk to the subject's health or the subject is unwilling to continue because of the AE.

- Liver Function Test (LFT) Abnormalities

Study medication should be discontinued immediately with appropriate clinical follow-up (including repeat laboratory tests, until a subject's laboratory profile has returned to normal/baseline status, see Section 9.1.8), if the following circumstances occur at any time during study medication treatment:

- ALT or AST $> 8 \times$ ULN, or

- ALT or AST $> 5 \times$ ULN and persists for more than 2 weeks, or
- ALT or AST $> 3 \times$ ULN in conjunction with elevated total bilirubin $> 2 \times$ ULN or international normalized ratio (INR) > 1.5 , or
- ALT or AST $> 3 \times$ ULN with appearance of fatigue, nausea, vomiting, right upper quadrant pain or tenderness, fever, rash and/or eosinophilia ($> 5\%$).

- Hypoestrogenic symptoms

The investigator or subinvestigator makes an overall risk-benefit assessment for the subject when any of the following events that can be considered related to the pharmacological effect of TAK-385 occur, and decides whether to stop the drug administration based on the intensity and frequency of the event:

- Hot flush, feeling hot, flushed face, shoulder stiffness, headache, insomnia, dizziness, perspiration, menopausal depression, decreased libido, feeling cold, visual disturbance, emotional lability, etc.
- ECG abnormality

The subject judged by the investigator or subinvestigator to be inappropriate for continuation of the study based on standard 12-lead ECG findings.

3. Protocol deviation. The discovery after randomization that the subject failed to meet protocol entry criteria or did not adhere to protocol requirements, and continued participation poses an unacceptable risk to the subject's health.
4. Lost to follow-up. The subject did not return to the clinic and attempts to contact the subject were unsuccessful. Attempts to contact the subject must be documented.
5. Withdrawal by subject. The subject wishes to withdraw from the study. The reason for withdrawal, if provided, should be recorded in the eCRF.

Note: All attempts should be made to determine the underlying reason for the withdrawal and, where possible, the primary underlying reason should be recorded (withdrawal due to an AE or lack of efficacy should not be recorded in the "Withdrawal by subject" category). If subject wishes to withdraw from the study to proceed to surgery, the category No.9 "Recovery leading to surgery" should be recorded.

6. Study terminated by sponsor. The sponsor terminates the study.
7. Pregnancy. The subject is found to be pregnant.

Note: If the subject is found to be pregnant, the subject must be withdrawn immediately. The procedure is described in Section 9.1.10.

8. Lack of efficacy. The investigator or subinvestigator judges TAK-385 shows no efficacy based on the menstrual blood loss, menstrual status, and use of analgesics (eg, a notable increase in menstrual blood loss after start of study drug administration) and judges continued participation in the study would pose an unacceptable risk to the subject.

9. Bone mineral density loss. The subjects with BMD measured by DXA at VISIT 7 is $< 90\%$ of baseline (or subjects with BMD changes from baseline $> 10\%$), or the investigator or subinvestigator makes an overall risk-benefit assessment for the subject and decides to stop the study drug administration, even if the subject's BMD maintains $\geq 90\%$ of baseline (or with a BMD change from baseline $\leq 10\%$).
10. Recovery leading to surgery. The subject who does not apply to any of the above category 1 to 8 and has a favorable outcome (eg, the improvement in the bleeding profile, the reduction in myoma and uterine volumes, and improvement in anemia) leading to the proceeding to surgery, and the investigator or subinvestigator judges that it is appropriate to proceed to surgery and not ethically desirable for the subject to be administered the study drug any longer.
11. Reduction of HGB concentration. Regardless of with or without iron preparations administration, HGB concentration of subject at VISIT 2 or later decreases to < 8.0 g/dL.
12. Other.

Note: The specific reasons should be recorded in the "specify" field of the eCRF.

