7.3.5 Disposition of Subjects

Analysis Set: Randomized Set

Analysis Double-blind study drug

Variable(s) : administration status [Randomized but Not Treated]
Reason for not being treated [Death, Adverse Event, Protocol Deviation, Lost to Follow-up, Withdrawal by Subject, Study Terminated by Sponsor, Pregnancy, Lack of Efficacy, Bone Mineral Density Loss, Recovery Leading to Surgery, Reduction of HGB Concentration, Other]
Double-Blind Study Drug [Completed Study Drug, Prematurely Discontinued Study Drug]
Completion Status

Reason for Discontinuation of Study Drug [Death, Adverse Event, Protocol Deviation, Lost to Follow-up, Withdrawal by Subject, Study Terminated by Sponsor, Pregnancy, Lack of Efficacy, Bone Mineral Density Loss, Recovery Leading to Surgery, Reduction of HGB Concentration, Other]

Completion Status of the Follow- [Completed Follow-up Period,

up Period	Prematurely Discontinued Follow-up Period]
Reason for Discontinuation of the Follow-up Period	[Death, Adverse Event, Protocol Deviation, Lost to Follow-up, Withdrawal by Subject, Study Terminated by Sponsor, Pregnancy, Lack of Efficacy, Bone Mineral Density Loss, Recovery Leading to Surgery, Reduction of HGB Concentration, Other]
Analytical	
Method(s) :	(1) Disposition of Subjects
	Frequency distributions will be provided for each treatment group and overall. When calculating percentages for the reasons for not being treated, the total number of subjects not treated by the study drug will be used as the denominator. When calculating percentages for the reasons for discontinuation, the total number of subjects who prematurely discontinued will be used as the denominator.

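### The note in Protocol 7.5 on withdrawal for surgery conflicts with categories 8, 9 and 10, so an exit for surgery after inadequate response can be recorded as a recovery

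*Protocol*

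**What the plan says.** Protocol 7.5 gives the categories in which the primary reason for discontinuation is entered in the eCRF. Four of them matter here.

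- **Category 5, withdrawal by the subject.** The note tells sites to look for the underlying reason and adds that "withdrawal due to an AE or lack of efficacy should not be recorded in the" category for withdrawal by the subject. It then says "If subject wishes to withdraw from the study to proceed to surgery, the category No.9", names that category in words as Recovery leading to surgery, and directs that it be recorded. It states no condition on outcome.
- **Category 8, lack of efficacy.** The investigator must see no efficacy and also "judges continued participation in the study would pose an unacceptable risk to the subject".
- **Category 9.** "9. Bone mineral density loss. The subjects with BMD measured by DXA at VISIT 7 is" below a stated fraction of baseline, or the investigator decides to stop on an overall risk-benefit assessment.
- **Category 10, Recovery leading to surgery.** It covers "The subject who does not apply to any of the above category 1 to 8 and has a favorable outcome", and it requires that "the investigator or subinvestigator judges that it is appropriate to proceed to surgery".

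SAP 7.3.5 tabulates the reasons for stopping study drug by arm and overall. Its list ends "Lack of Efficacy, Bone Mineral Density Loss, Recovery Leading to Surgery, Reduction of HGB Concentration, Other". The entries are text labels without numbers, and the denominator for the percentages is the number of subjects who stopped prematurely.

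**The concern.** Surgery is a foreseeable reason to leave. Protocol 6.2.1 describes drug treatment before surgery with a usual presurgical period of 3 months, while treatment here lasts 24 weeks. Protocol 7.3.3 prohibits fibroid surgery during the study unless the woman has terminated early.

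Such an exit can mean opposite things: treatment worked well enough to operate, or it did not work and the woman chose surgery instead. The reason code is where the disposition table makes that distinction. If the rule that assigns the code contradicts itself, some failures may be tabulated as recoveries, and sites may resolve the contradiction differently. A wrong category number that happens to belong to BMD loss adds a second possible error, in a reason that bears on a safety question of the 24-week period.

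**Working it through.** The plan states no figure on this point, so the check is a reading of the rules side by side.

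**Step 1: numbering.** Counting the list in Protocol 7.5 gives 12 categories: 8 is lack of efficacy, 9 is BMD loss, 10 is Recovery leading to surgery. The SAP 7.3.5 list also has 12 entries, in the same order. The note's number is therefore one too low, and the range in category 10 stops one short of the items above it. Both would be right if Recovery were No.9. That would fit an item having been inserted without updating the references, but this is an inference.

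**Step 2: run typical exits through the text.**

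| Exit | Category 5 note | Category 8 | Category 9 | Category 10 |
|---|---|---|---|---|
| A. Favourable outcome, woman wishes to have surgery, investigator agrees | Recovery by name, BMD loss by number | Not met | Not met | Conditions met, but literally barred because 5 lies within 1 to 8 |
| B. Inadequate response, woman chooses surgery, no judgement of unacceptable risk | Recovery by name, BMD loss by number | Not met (risk condition fails) | Not met | Not met (no favourable outcome) |
| C. Inadequate response, investigator judges no efficacy and unacceptable risk | Surgery sentence says Recovery; the underlying-reason instruction keeps lack of efficacy out of 5 | Met | Not met | Excluded by 8 |
| D. BMD criterion met, favourable bleeding outcome, goes on to surgery | Applies only if she initiates the exit | Not met | Met | Not excluded, because the range omits 9 |

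Exit B is the substantive gap. She meets the full wording of neither 8 nor 10, and the only explicit instruction for her surgery is the note, which gives the Recovery label. Exit A shows the circularity, and exit D the overlap.

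**Step 3: where the code is used.** In the documents provided, the reasons feed the descriptive table in SAP 7.3.5. Response is computed from the diary (SAP 7.1.1), not from the reason for stopping.

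**Step 4: sensitivity of the table.** With D premature discontinuations in an arm, each misrouted exit moves a reason's percentage by 100/D points. D is not given. As an assumption only, borrow the allowance for non-evaluable subjects: 10% × 144 = 14.4, and 144 − 129 = 15, so take D = 14 to 15.

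- 1 exit: 1/15 = 6.7% to 1/14 = 7.1%
- 2 exits: 2/15 = 13.3% to 2/14 = 14.3%
- 3 exits: 3/15 = 20.0% to 3/14 = 21.4%

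The allowance concerns evaluability for the primary endpoint, not early stopping, so this shows only how coarse the table is. Dividing by 144 (2/144 = 1.4%) would use the wrong denominator for this table.

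**The case against.** The case for treating this as a wording slip is strong in several respects.

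- **The name settles the number.** The note spells out Recovery leading to surgery, and the SAP uses unnumbered labels. Coding to BMD loss needs a site or eCRF that follows the number against the name, and the eCRF is not in the documents. This stands: it is a risk, not what the plan directs.
- **The note also asks for the underlying reason.** It keeps adverse events and lack of efficacy out of category 5, and category 10 excludes anyone who meets category 8. This disposes of exit C. It does not dispose of exit B, because category 8 is not met and the surgery sentence pulls the other way.
- **Circularity and overlap can be read away.** The note can be taken as a specific instruction that moves surgery exits out of category 5, and only one primary reason is recorded. That is the sensible reading, but the text does not state it, and it does not say whether 9 or 10 takes precedence.
- **The outcomes are analysed independently.** PBAC for the last 6 weeks of treatment (SAP 7.8.2.1), HGB (7.8.2.3) and BMD change (7.11.5.1) are summarised by arm, and BMD is scheduled at early termination. This stands, although no cross-tabulation with reason for stopping is planned.

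A reader might infer that every woman who leaves for surgery is coded as BMD loss, or as a recovery whatever happened, and that the table therefore cannot separate success, failure and bone loss. The documents do not support this. The surgery sentence concerns withdrawal initiated by the subject, the three reasons are separate SAP entries, and the gap is the narrower one in exit B.

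**Conclusion.** The point holds as a recording defect. Protocol 7.5 contradicts itself on the cross-reference, on the conditions for the Recovery label, and on the range that separates category 10 from 5 and 9. Its clearest consequence is that a subject-initiated exit for surgery after inadequate response, without a judgement of unacceptable risk, is labelled as a recovery if the note is followed literally.

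The size cannot be stated because the documents give no count of such exits. Surgery being a common exit is an inference from the treatment setting; no inclusion criterion requires planned surgery.

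The reach is limited to the by-arm reasons in SAP 7.3.5. A reader might infer that failures would be counted as successes in the efficacy results. They would not: response does not use the codes, and the SAP contains no analysis that classifies early stoppers by reason. Its named robustness analysis is the per protocol set (7.8.1.2). The full definition of that set is in the Handling Rules, which were not available, so this conclusion assumes that those rules do not use the codes. It is worth correcting because it is cheap and the table would otherwise mislead.

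**What to change.** Change the recording text only:

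1. Correct the category 5 note to cite No.10.
2. Make the note apply only when category 10's own favourable-outcome condition is met.
3. Correct the range in category 10 so that 9 and 10 do not overlap. State that a withdrawal redirected by the note is not treated as category 5 for this purpose; extending the range alone would leave the circularity.
4. Reconcile categories 5, 8, 9 and 10 so that surgery after a favourable outcome, surgery after inadequate response, and BMD loss are recorded distinctly. The stopping criteria in category 8 and elsewhere stay as they are. Protocol 7.6 treats Section 7.5 as the termination criteria, so loosening category 8 to capture exit B would change more than the recording.
5. In the blinded data review already planned in Protocol 13.1, check the recorded reason for each exit to surgery against the PBAC, HGB and BMD data, and query inconsistencies before unblinding.

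The cost is a wording amendment to the protocol and eCRF guidance and a short query round. It needs no new assessments and adds no burden for subjects.

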7.6 Procedures for Discontinuation or Withdrawal of a Subject

The investigator or subinvestigator may discontinue a subject's study participation at any time during the study when the subject meets the study termination criteria described in Section 7.5. In addition, a subject may discontinue her participation without giving a reason at any time during the study. Should a subject's participation be discontinued, the primary criterion for termination must be recorded by the investigator or subinvestigator. In addition, efforts should be made to perform all procedures scheduled for the Early Termination Visit. Discontinued or withdrawn subjects will not be replaced.

8.0 CLINICAL TRIAL MATERIAL MANAGEMENT

This section contains information regarding all medication and materials provided directly by the sponsor, and/or sourced by other means, that are required by the study protocol, including important sections describing the management of clinical trial material.

8.1 Study Medication and Materials

8.1.1 Dosage Form, Manufacturing, Packaging, and Labeling

8.1.1.1 Investigational Drug

1. TAK-385

Study drug name: TAK-385

Nonproprietary name: relugolix (international non-proprietary name [INN])

Chemical name:

Urea,N-[4-[1-[(2,6-difluorophenyl)methyl]-5-[(dimethylamino)methyl]-1,2,3,4-tetrahydro-3-(6-methoxy-3-pyridazinyl)-2,4-dioxothieno[2,3-d]pyrimidin-6-yl]phenyl]-N'-methoxy-

Dosage form and content:

Name	Content
TAK-385 40 mg tablet	Contains 40 mg of TAK-385 per tablet
TAK-385 placebo tablet	Contains no TAK-385 per tablet

Appearance: both the TAK-385 40 mg tablet and TAK-385 placebo tablet are light yellow red, film-coated tablets and are indistinguishable in appearance from each other.

2. Leuprorelin

Study drug name: leuprorelin acetate

Nonproprietary name: leuprorelin (INN)

Chemical name:

5-Oxo-prolyl-histidyl-tryptophyl-seryl-tyrosyl-D-leucyl-leucyl-arginyl-N-ethyl-prolinamide monoacetate

Dosage form and content:

Name	Content
Leuprorelin acetate 1.88 mg injection	Contains 1.88 mg of leuprorelin per vial
Leuprorelin acetate 3.75 mg injection	Contains 3.75 mg of leuprorelin per vial
Leuprorelin acetate 1.88 mg placebo injection	Contains no leuprorelin per vial
Leuprorelin acetate 3.75 mg placebo injection	Contains no leuprorelin per vial

CONFIDENTIAL

Appearance: the powder for both of the leuprorelin acetate 1.88 mg injection and the corresponding placebo injection, and the powder for both of the leuprorelin acetate 3.75 mg injection and the corresponding placebo injection are indistinguishable in appearance from each other. The vials filled with them are also indistinguishable from each other.

3. Vehicle for suspension

An ampule (1 mL) contains water for injection, and 50 mg of D-mannitol, 5 mg of carmellose sodium, and 1 mg of polysorbate 80 as excipients.

8.1.1.2 Packaging and Labeling

1. Packaging of study drugs for the Run-in (single-blind)

1) TAK-385

TAK-385 placebo tablets are packaged in blister cards containing 14 tablets (for 14 days) per sheet. Three blister cards are sealed in an aluminum pouch with desiccant. Three aluminum pouches, each containing 3 blister cards, are placed in an outer case. One pouch is allocated to each subject.

The outer case indicates that it contains a study drug and includes the name of the drug, quantity, protocol number, sponsor's name and address, serial number, and storage conditions.

2) Leuprorelin

One vial of leuprorelin acetate 1.88 mg placebo injection or leuprorelin acetate 3.75 mg placebo injection and an ampule of vehicle for suspension (for one injection) are contained in a small box. One small box is allocated to each subject.

The small box indicates that it contains a study drug and includes the name of the drug, protocol number, sponsor's name and address, serial number, and storage conditions.

2. Packaging of study drugs for the Treatment (double-blind)

1) TAK-385

TAK-385 40 mg tablets or TAK-385 placebo tablets are packaged in blister cards containing 14 tablets (for 14 days) per sheet. Three blister cards are sealed in an aluminum pouch with desiccant. Six aluminum pouches, each containing 3 blister cards, are placed in an outer case. One outer case is allocated to each subject. All packaging materials for TAK-385 40 mg tablets and TAK-385 placebo tablets are indistinguishable from each other.

The outer case indicates that it contains a study drug, and includes the name of the drug, quantity, protocol number, sponsor's name and address, serial number, and storage conditions.

2) Leuprorelin

One vial of leuprorelin acetate (1.88 mg, 3.75 mg, 1.88 mg placebo, or 3.75 mg placebo) injection and an ampule of vehicle for suspension (for one injection) are contained in a small box. One vial of leuprorelin acetate (1.88 mg, 3.75 mg, 1.88 mg placebo, or 3.75 mg placebo) injection and 3 ampules of vehicle for suspension are contained in a small box as a spare. Eight

small boxes (6 boxes for scheduled once-use and 2 boxes for spare use) are placed in an outer case. One outer case is allocated to each subject. All packaging materials for leuprorelin are indistinguishable from each other.

The outer case indicates that it contains a study drug and includes the name of the drug, quantity, protocol number, sponsor's name and address, serial number, and storage conditions.

8.1.2 Storage

All investigational drugs referred in [8.1.1.1](#) are to be kept at room temperature (1°C to 30°C). A daily temperature log of the drug storage area must be maintained every working day.

Investigational drugs must be kept in an appropriate, limited-access, secure place until it is used or returned to the sponsor or designee for destruction. Investigational drugs must be stored under the conditions specified on the label, and remain in the original container until dispensed.

Leuprorelin acetate (1.88 mg or 3.75 mg) injection, leuprorelin acetate (1.88 mg or 3.75 mg) placebo injection and their vehicle for suspension are to be kept in the original containers until use.

8.1.3 Dose and Regimen

[Table 8.a](#) describes the dose and tablet count that will be provided to each group.

Table 8.a Dose and Regimen

Period	Group	Dose and Regimen
Run-in	All group	
• One TAK-385 placebo tablet per day• One leuprorelin acetate (1.88 mg or 3.75 mg) placebo injection once/4 weeks
Treatment	TAK-385 40 mg group	
• One TAK-385 40 mg tablet per day• One leuprorelin acetate (1.88 mg or 3.75 mg) placebo injection once/4 weeks
	Leuprorelin group	
• One TAK-385 placebo tablet per day• One leuprorelin acetate (1.88 mg or 3.75 mg) injection once/4 weeks

1. TAK-385
 - 1) Run-in
Administration of TAK-385 placebo tablets should be started on the day of VISIT 2. Until the day before VISIT 3, subjects take 1 tablet once daily before breakfast. The investigator or designee must instruct the subject to bring each of the study drug containers (blister cards) to each visit, regardless of whether the study drugs are empty.
 - 2) Treatment
Administration of TAK-385 40 mg tablets or TAK-385 placebo tablets should be started on the day of VISIT 3. Until the day before VISIT 10, subjects take 1 tablet once daily before breakfast.

CONFIDENTIAL

During the Treatment, subjects should try to make each scheduled visit to the study site in the morning and take the TAK-385 (40 mg or placebo) tablet for the day after completing the scheduled tests (see Section 7.4). However, if unable to visit the study site in the morning of VISIT 4, 5, 6, 7, 8 or 9, subjects should take the morning dose before breakfast and report to the investigator or subinvestigator that the morning dose has been taken (see Section 7.4).

2. Leuprorelin
 - 1) Run-in
- 1) Run-in

The investigator or subinvestigator will decide the dosage of leuprorelin acetate (1.88 mg or 3.75 mg) injection for individual subjects at VISIT 2 (see Section 6.1.2 for details). Leuprorelin acetate (1.88 mg or 3.75 mg) placebo injection should be administered SC on the day of VISIT 2.

- 2) Treatment

Leuprorelin acetate (1.88 mg, 3.75 mg, 1.88 mg placebo, or 3.75 mg placebo) injection are administered SC once every 4 weeks on the day of visiting the study sites. At VISIT 4, leuprorelin acetate (1.88 mg, 3.75 mg, 1.88 mg placebo, or 3.75 mg placebo) injection should NOT be administered.

For dosing, powder in a vial should be sufficiently suspended with the vehicle for suspension (1 mL). A needle for injection of 23 Gauge or larger should be used. For optimal SC injection, need to follow the following instructions.

- The site for SC injection should be the brachial, abdominal or gluteal region.
- The injection site should be changed each time. Repeated injection should not be given at the same site.
- Confirmation should be made to see that the needle is not piercing a blood vessel.
- The patients should be instructed not to massage the injection site.

Instructions for preparing method of leuprorelin acetate (1.88 mg or 3.75 mg) injection and leuprorelin acetate (1.88 mg or 3.75 mg) placebo injections are as follows.

- The injectable solution should be prepared at the time of use and be used immediately after preparing the suspension.
- If any sedimentation is noticed in the suspension of vial product, such suspension should be used after swirling the vial gently, avoiding formation of bubbles, to resuspend the particles uniformly.

